## **9.5. Handling of Missing Data**

The primary endpoint of craving cannot be imputed; likewise, for the other craving questions given during the human lab session. Secondary endpoints analyzed with mixed effects or logistic regression models are capable of handling missing data, so no imputation will be utilized. PROMIS scores are analyzed using ANCOVA which cannot handle missing data; therefore, only subjects with an assessment during the treatment period will be used and no imputation.

## **9.6. Safety Analysis**

### **9.6.1. Adverse Events**

AEs will be coded using the most recent version of the Medical Dictionary for Regulatory Activities (MedDRA) and will be grouped by system, organ, and class (SOC) and preferred term (PT) designation. The severity, frequency, and relationship of AEs to investigational product will be presented by SOC and PT groupings. Listings of each individual AE including start date, stop date, severity, relationship, outcome, and duration will be provided. Each AE (based on PT) will be counted once only for a given study subject. If the same AE occurred on multiple occasions, the highest severity will be assumed. Thus, study subjects are not counted multiple times in a given numerator in the calculation of frequencies for a specific AE. C-SSRS reports of suicidality or suicidal ideation will be reported as AEs and analyzed as AEs if the investigator determines after an interview with the subject, that the responses are consistent with suicidal ideation or attempt.

### **9.6.2. Clinical Laboratory and Point of Care Tests**

For clinical laboratory data, descriptive statistics will be generated for all tests performed at screening and at each clinic visit. If a laboratory analysis is repeated, the last measurement performed prior to the clinic visit will be used in the summary statistics for that clinic visit. If an unscheduled clinical laboratory visit occurs prior to a scheduled visit that is missed due to dropout, then the unscheduled visit will be used in the summary statistics for the missed scheduled clinical visit. If an unscheduled clinical laboratory visit occurs between two scheduled clinical visits, then the data from the unscheduled visit only be presented in the listings and not in summary statistics. In addition, at each post-randomization clinic visit descriptive statistics for change from baseline will be generated. Laboratory values will be plotted as mean  $\pm$  standard error over time. All laboratory measurements will be presented in the listings.

Number and percentage of positive urine drug tests and pregnancy tests for screening visits and all treatment and follow-up visits will be tabulated. Results of all urine drug tests and pregnancy tests will be presented in the listings. The percentage of subjects with a positive urine drug test at any time post start of treatment will also be presented by test type and treatment group.

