a EOS - end of study. These assessments are to be done at Week 7 or if the subject discontinues early and agrees to a final clinic visit.

b Within each study week, there should be a least two days elapsed since the visit in the prior week.

- c Test for opiates (i.e., morphine test), cocaine, amphetamines, methamphetamine, THC, buprenorphine, methadone, benzodiazepines, oxycodone, barbiturates, 3,4-methylenedioxy-methamphetamine (MDMA – also known as ecstasy), and EtG.
- d Creatinine, urea nitrogen, total bilirubin, ALT, AST, alkaline phosphatase, GGT, albumin, total cholesterol, triglycerides, sodium, potassium, and chloride
- e Complete blood cell count including RBC, WBC, hemoglobin, hematocrit, and platelets.
- f A dipstick urinalysis will be performed that tests for specific gravity, ketones, pH, protein, blood, glucose, nitrites, bilirubin, and leukocyte esterase. If the dipstick is positive for blood, leukocyte esterase, or protein, then a microscopic analysis will be performed at the discretion of the investigator.
- g Sitting blood pressure and heart rate.
- h Telephone calls after the Week 1 and 2 in clinic visits will collect AEs, concomitant medications, CIWA-AR, and give a drug compliance reminder. The call during Week 2 should be several days before the cue session to remind the subject of the planned visit.
- i Two modules will be viewed this week.

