**Table 123: Summary of Blood Chemistry and Hematology – Safety Subjects**

	ASP8062				Placebo			
	N	Mean (SD)	Med	(Min-Max)	N	Mean (SD)	Med	(Min-Max)
Chemistry (units)								
Baseline Value	xx	xx.x (xx.x)	xx.x	(xx.x-xx.x)	xx	xx.x (xx.x)	xx.x	(xx.x-xx.x)
Week 4	xx	xx.x (xx.x)	xx.x	(xx.x-xx.x)	xx	xx.x (xx.x)	xx.x	(xx.x-xx.x)
Change from baseline	xx	xx.x (xx.x)	xx.x	(xx.x-xx.x)	xx	xx.x (xx.x)	xx.x	(xx.x-xx.x)
Week 7	xx	xx.x (xx.x)	xx.x	(xx.x-xx.x)	xx	xx.x (xx.x)	xx.x	(xx.x-xx.x)
Change from baseline	xx	xx.x (xx.x)	xx.x	(xx.x-xx.x)	xx	xx.x (xx.x)	xx.x	(xx.x-xx.x)

Programmers note: table will include creatinine, ALT, AST, total bilirubin, alkaline phosphate, albumin, CrCl, GGT, *RBC, WBC, hematocrit, hemoglobin, platelets*.

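### Unscheduled laboratory results between visits go to listings only and no table counts any-time abnormalities, so a transient one can be missing from the by-arm summaries

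*SAP*

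**What the plan says.** SAP section 9.6.2 sets three rules for results outside the planned draw.

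- Repeats: "If a laboratory analysis is repeated, the last measurement performed prior to the clinic visit will be used in the summary statistics" for that visit.
- Unscheduled result ahead of a scheduled visit that is missed because of dropout: "then the unscheduled visit will be used in the summary statistics for the missed scheduled clinical visit".
- Unscheduled result between two scheduled visits: "then the data from the unscheduled visit only be presented in the listings and not in summary statistics".

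It adds that "All laboratory measurements will be presented in the listings".

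The Schedule of Assessments (SAP Table 1) places chemistry and hematology at screening, Week 4 and Week 7. The Table 123 shell gives N, mean (SD), median, min-max and change from baseline at those times. Listing 29 carries a high/low flag for each chemistry result and an evaluation as within normal limits, abnormal but not clinically significant, or abnormal and clinically significant. Listing 30 (hematology) shows neither column.

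**The concern.** A by-visit summary with two post-dose time points shows only what was present on those two occasions. Results from other days come from extra samples, and the third rule sends those to the listings unless a visit was lost to dropout. If extra samples are often drawn because something looked wrong (a reasonable assumption, but not stated in either document), the excluded results are the ones a safety reader most wants to see compared by arm.

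A listing keeps the value but gives no count by arm. Min-max in Table 123 cannot show a value that the rule kept out of the table. At stake is whether a short-lived laboratory abnormality on an investigational drug, in heavy drinkers, is visible in the safety tables.

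**Working it through.** No plan figure needs reproducing here. The check sets the rules against the schedule and the table shells.

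**1. Intervals without a scheduled draw.** Dosing starts on Day 1; Week 4 is Days 22 to 28 and Week 7 is Days 43 to 49 (SAP Table 1).
- Day 1 to the Week 4 draw: 22 − 1 = 21 to 28 − 1 = 27 days.
- Week 4 draw to Week 7 draw: 43 − 28 = 15 to 49 − 22 = 27 days.

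**2. Where each kind of result ends up.**

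| Situation | Treatment under 9.6.2 | Result |
|---|---|---|
| Abnormal value, repeated before the visit being summarised | Last value before the visit is used | Earlier value is in listings only |
| Abnormal at Week 4, repeated before an attended Week 7 visit | Not stated outright; most naturally the repeat is an in-between result | Week 4 value stays in Table 123; repeat is listed |
| Abnormal at Week 7, repeated later | Repeat does not precede the Week 7 visit | Week 7 value stays in Table 123 |
| Unscheduled, later scheduled visit missed through dropout | Used for the missed visit | In Table 123 |
| Unscheduled, between two scheduled visits | Listings only | In no laboratory table |

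Only the first and last rows lose a value. The clearest instance of the first row is a repeat at screening, which affects only the pre-dose baseline. The last row therefore carries the point.

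**3. Safety tables that could recover the lost value.** Among Tables 110 to 129, the number giving a worst post-dose value, a shift, a threshold count or a clinical-significance count for chemistry or hematology is 0. The SAP does use such summaries for other safety measures:
- adverse events at highest severity (9.6.1);
- CIWA-AR of 10 or more at any time after dosing starts (9.6.4, Table 120);
- positive urine drug tests at any time after treatment starts (9.6.2);
- BAC above 0.02 and suicidal ideation at any time during the study (Tables 127 and 128);
- ECG by clinical significance (9.6.3, Table 122).

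**4. Scale.** With 30 subjects planned per arm, 1/30 = 3.3%. This is the weight of one subject in a count, not an estimate of bias.

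**5. Which tests are tabulated.** The text promises that "descriptive statistics will be generated for all tests performed at screening and at each clinic visit". The schedule's chemistry footnote lists 13: "Creatinine, urea nitrogen, total bilirubin, ALT, AST, alkaline phosphatase, GGT, albumin, total cholesterol, triglycerides, sodium, potassium, and chloride". The Table 123 note says "table will include creatinine, ALT, AST, total bilirubin, alkaline phosphate, albumin, CrCl, GGT", followed by the hematology tests. That is 7 of the 13 plus derived creatinine clearance, so 13 − 7 = 6 chemistry tests (urea nitrogen, total cholesterol, triglycerides, sodium, potassium, chloride) have no table shell. This is a separate mismatch, but it bears on the fix, because added rows per test need a stated list of tests.

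**The case against.** The other side has a good deal of substance.

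- A reader might infer that unscheduled results are excluded from all summaries. They are not: 9.6.2 uses them when a scheduled visit is missed through dropout.
- A reader might infer that repeats routinely displace the abnormal value that prompted them, pulling the summaries toward normal. The documents do not support this for post-dose data. A repeat after an abnormal Week 4 or Week 7 draw does not precede that visit, so on the natural reading the abnormal value stays in Table 123, where min-max shows it if it is the extreme. The SAP does not say so in terms, and that gap is worth closing.
- A reader might infer that a raised liver test that normalises would appear in no table. If it was drawn at Week 4 or 7, that is wrong on the same reading: ALT, AST, total bilirubin and GGT are all in Table 123.
- There are other routes. Dipstick results are tabulated by category (Tables 125 and 126), and an abnormality recorded as an adverse event reaches Tables 110 to 119. The protocol text available is the synopsis, so the rule for recording a laboratory abnormality as an adverse event cannot be checked.
- Every value is listed, and with 60 subjects the listings can be read in full.

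All of this stands, and it narrows the point. It does not remove the case of an unscheduled between-visit result that was not recorded as an adverse event: no by-arm summary would include it.

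**Conclusion.** The concern holds in a limited form. Unscheduled results between scheduled visits, and any value superseded by a repeat done before the visit being summarised, appear only in listings. No table gives worst post-dose values or counts clinically significant chemistry results by arm. A transient abnormality between visits can therefore be missing from all by-arm summaries, provided that it was not recorded as an adverse event and that no visit was missed through dropout so as to bring it in.

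Its frequency cannot be estimated from the documents, and nothing here shows a systematic shift toward normal values. Efficacy results, sample size and power are unaffected. This is a gap in presentation, worth closing because the SAP already uses any-time or clinical-significance counts for its other safety measures. Label: cheap improvement.

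**What to change.** Keep the by-visit rule for Table 123. Add by arm, on the safety set, using all scheduled, repeat and unscheduled post-dose samples:

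1. the worst post-dose value for each chemistry and hematology test, naming the tests and stating the direction (highest, lowest, or both for tests where either extreme matters);
2. the number and percentage of subjects with any post-dose chemistry result evaluated as abnormal and clinically significant.

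Also state in 9.6.2 that a repeat done after a scheduled visit does not replace that visit's value.

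The cost is a few extra table rows from data already collected. Hematology gets worst values only, unless a significance evaluation is recorded for it, since Listing 30 shows none.

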### **9.6.3. Vital Signs, ECG, and Body Weight**

Vital signs will be presented as summary statistics and change from baseline. The percentage of ECG results considered abnormal and clinically significant will be provided. Body weight will be presented as summary statistics and change from screening. Vital signs, ECG results, and weight measurements for all visits will be presented in the listings.

#### **9.6.4. CIWA-AR Scores**

The number and percentage of subjects who reported CIWA-AR scores  $\geq 10$  at any time after the start of dosing will be presented.

#### **9.6.5. ACQ-SF-R Scores**

Summary statistics for ACQ-SF-R raw scores prior to after each cue session will be presented. The number and percentage of subjects with a higher ACQ-SF-R score post each cue session will be provided by treatment group.

### **9.7. Drug Exposure and Retention Analyses**

Drug exposure will be presented for each treatment group as the mean number of tablets taken by week and overall through AiCure during the entire treatment phase. The analysis will include the total number of tablets taken and the percent compliance. AiCure data will also be used for the number subjects receiving reminder intervention (phone calls, texts, or in person visits). Compliance will also be evaluated by determining the proportion of subjects who were prescribed ASP8062, reported taking ASP8062 (by AiCure assessment), and had a plasma sample with detectable ASP8062. Compliance by ASP8062 plasma levels will be reported as number and percentage of subjects with a level above the limit of detection at each time point. Descriptive statistics of plasma levels of ASP8062 and metabolites will also be provided. Samples with levels below of limit of quantitation will not be included in the summary statistics and the N will reflect the number with a detectable level at each timepoint.

The participation rate is the percentage of subjects with complete drinking data. Dropouts by week with cumulative percentages will be provided by treatment arm.

### **9.8. Blood Alcohol Content**

The number and percentage of subjects at any clinic visit that have a BAC  $> 0$  will be tabulated. All BAC measurements will be presented in the listings.

### **9.9. Exploratory and Ad Hoc Analyses**

#### **9.9.1. Hyperkatifeia Scale**

There is interest in exploring the use of a new Hyperkatifeia Scale as a predictor of drug response and possibly as an outcome measure. *Ad hoc* analyses will be performed on this scale as a planned part of exploring the utility of this scale including subscales and individual items. *Ad hoc* analyses may include: 1) examining the association between cue outcomes and naturalistic outcomes; 2) conducting of moderator analyses; and 3) examining the treatment goal assessment and its relationship between outcomes. The data from this study could be used for combined analyses with results of other studies conducted in the future.

#### **9.9.2. Supplemental Exploratory Analysis**

The exploratory analysis are defined as: Explore moderators of the treatment effect on primary and secondary outcomes. The exploratory endpoint will not be analyzed at the same time as the primary and secondary endpoints.

## **10. VALIDATION OF PROGRAMMING CODE**

All SAS codes used to generate tables and listings will be validated and reviewed before being finalized. The validation process will be used to determine that the numbers are produced by a statistically valid method and that the execution of the computations is correct. Qualified personnel who have not previously been involved in the production of the original programming codes will perform the validation procedures. Methods of validation include independent programming and comparison to data listings. Tables will be reviewed for accuracy, consistency with this plan, consistency within tables, and consistency with corresponding output. Once validation is complete, a quality control reviewer will perform a final review of the documents for accuracy and consistency. Upon completion of validation and quality review procedures, all documentation will be collected and filed in the study documentation files at Fast-Track.

**12. TABLE, LISTING, AND FIGURE SHELLS**

**12.1. Tables**

**12.1.1. Subject Disposition, Participation, Compliance**

**Table 1: Subject Disposition - All Randomized Subjects**

	ASP8062 n (%)	Placebo n (%)	Total n (%)	p-value 
Number of Subjects Consented			xx	
Number of Subjects Screen Failed			xx	
Number of Subjects Randomized 	xx	xx	xx	0.xxx
Number of Subjects Randomized not Receiving Study Drug	x (xx.x)	x (xx.x)	x (xx.x)	0.xxx
Number of mITT Subjects	xx (xx.x)	xx (xx.x)	xxx (xx.x)	0.xxx
Number of Completed  Subjects	xx (xx.x)	xx (xx.x)	xxx (xx.x)	0.xxx
Number of Evaluable Subjects	xx (xx.x)	xx (xx.x)	xxx (xx.x)	0.xxx
Number of Subject Completing Study & Drug	xx (xx.x)	xx (xx.x)	xx (xx.x)	0.xxx
Number of Subjects Discontinuing Study Drug, Remaining in Study	xx (xx.x)	xx (xx.x)	xx (xx.x)	0.xxx
Number of Subjects Withdrawn Early (did not provide any data at Week 7)	xx (xx.x)	xx (xx.x)	xx (xx.x)	0.xxx
Reason for Early Withdrawal 				
Subject withdrew consent	xx (xx.x)	xx (xx.x)	xx (xx.x)	
Investigator withdrew subject	xx (xx.x)	xx (xx.x)	xx (xx.x)	
Lost-to-followup	xx (xx.x)	xx (xx.x)	xx (xx.x)	
Adverse Event	xx (xx.x)	xx (xx.x)	xx (xx.x)	
Increased drinking	xx (xx.x)	xx (xx.x)	xx (xx.x)	
Psychiatric crisis	xx (xx.x)	xx (xx.x)	xx (xx.x)	
Died	xx (xx.x)	xx (xx.x)	xx (xx.x)	
Absent from the protocol due to confinement in a controlled environment	xx (xx.x)	xx (xx.x)	xx (xx.x)	
Determined after randomization to be ineligible	xx (xx.x)	xx (xx.x)	xx (xx.x)	

Notes:  p-value from Fisher's exact test.

The following percentages are based upon number randomized

Completed is defined as attending all clinical visits through Week 7 making the subject available for all endpoint analyses

The following categories sum to the number of early withdrawals

*Programmer Notes: The discontinuation reasons are as given on the CRF. Include only the reasons actually used for the subjects in the study. If a subject discontinued, but the specific reason is missing, include 'Missing' as a row in the table. Use the order of discontinuation reasons as presented on the CRF page.*

**Table 2: Exposure to Investigational Products Using AICure Data – mITT Subjects**

	Number of Tablets Taken								
	ASP8062 N=XX				Placebo N=XX				
	N	Mean (SD  )	Med	(Min-Max)	N	Mean (SD)	Med	(Min-Max)	p-value 
Week 1	xx	xx.x (xx.x)	xx.x	(xx.x-xx.x)	xx	xx.x (xx.x)	xx.x	(xx.x-xx.x)	0.xxx
Week 2	xx	xx.x (xx.x)	xx.x	(xx.x-xx.x)	xx	xx.x (xx.x)	xx.x	(xx.x-xx.x)	0.xxx
Week 3	xx	xx.x (xx.x)	xx.x	(xx.x-xx.x)	xx	xx.x (xx.x)	xx.x	(xx.x-xx.x)	0.xxx
Week 4	xx	xx.x (xx.x)	xx.x	(xx.x-xx.x)	xx	xx.x (xx.x)	xx.x	(xx.x-xx.x)	0.xxx
Week 5	xx	xx.x (xx.x)	xx.x	(xx.x-xx.x)	xx	xx.x (xx.x)	xx.x	(xx.x-xx.x)	0.xxx
Week 6	xx	xx.x (xx.x)	xx.x	(xx.x-xx.x)	xx	xx.x (xx.x)	xx.x	(xx.x-xx.x)	0.xxx
Total Dose 	xx	xx.x (xx.x)	xx.x	(xx.x-xx.x)	xx	xx.x (xx.x)	xx.x	(xx.x-xx.x)	0.xxx

 p-value from t-test Dose is the total number of tablets taken, maximum prescribed is 42 tablets SD is standard deviation**Table 3: Total Exposure to Investigational Products Using AICure Data – Evaluable Subjects**

Same as Table 2 only using evaluable subjects

**Table 4: Compliance to Investigational Products Using AiCure Data – mITT Subjects**

Same analysis as Table 2 using compliance rather than dose. Compliance is the number of capsules taken/number of capsules prescribed.

**Table 5: Compliance to Investigational Products Using AiCure Data – Evaluable Subjects**

Same analysis as Table 4 using evaluable subjects

**Table 6: AiCure Interventions mITT Subjects**

	ASP8062		Placebo	
	N	# Receiving $\geq 1$	N	# Receiving $\geq 1$
Interventions 	xx	xx	xx	xx

 Interventions includes texts, emails, and phone calls

**Table 7: AiCure Interventions – Evaluable Subjects**

Same as Table 6 only using evaluable subjects

**Table 8: Summary of ASP8062 and Metabolite Plasma Levels – ASP8062 Arm Only (mITT Subjects)**

	ASP8062			
	N	% > LLD	Mean (SD)	(Min-Max)
Week 4	xx	xx.x	xx.x (xx.x)	(xx.x-xx.x)
Week 7	xx	xx.x	xx.x (xx.x)	(xx.x-xx.x)
AS3486189				
	N	% > LLD	Mean (SD)	(Min-Max)
Week 4	xx	xx.x	xx.x (xx.x)	(xx.x-xx.x)
Week 7	xx	xx.x	xx.x (xx.x)	(xx.x-xx.x)
AS3486191				
	N	% > LLD	Mean (SD)	(Min-Max)
Week 4	xx	xx.x	xx.x (xx.x)	(xx.x-xx.x)
Week 7	xx	xx.x	xx.x (xx.x)	(xx.x-xx.x)
AS3486192				
	N	% > LLD	Mean (SD)	(Min-Max)
Week 4	xx	xx.x	xx.x (xx.x)	(xx.x-xx.x)
Week 7	xx	xx.x	xx.x (xx.x)	(xx.x-xx.x)

 LLD is lowest level of detection SD is standard deviation

**Table 9: Summary of ASP8062 Plasma Levels – ASP8062 Arm Only (Evaluable Subjects)**

Same as Table 8 only using evaluable subjects.

**Table 10: AiCure Report of ASP8062 Versus ASP8062 Plasma Levels – mITT Subjects**

		AiCure Report Indicates Drug Taken (pill count must = 1, on the day before the blood sample was drawn)			
Timing	Plasma level Indicates Drug Taken a	Yes, n (%)	No, n (%)	p-value b	kappa c
Week 4	Yes				
	No				
Week 7	Yes				
	No				
Overall	Yes				
	No				

a Blood level of  $\geq$ xx ng/mL indicates drug taken

b Chi-square test for independence

c Kappa test for agreement

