
Number of Subjects (Planned): 60
Main Inclusion/Exclusion Criteria: Subjects will be male and female at least 21 years of age with 4 or more DSM-5™ symptoms of AUD (moderate to severe AUD). They must also be seeking treatment for AUD and if male, report drinking an average of at least 28 drinks per week or if female report drinking an average of at least 21 drinks per week prior to consent, and have at least 1 heavy drinking day (4 or more drinks per day for women/5 or more drinks per day for men) during the 7-day period prior to randomization.
Investigational Product, Dosage and Mode of Administration: The target doses are 25 mg tablet of ASP8062 by oral administration once daily at bedtime for 6 weeks.
Reference Therapy, Dosage and Mode of Administration: Subjects in the placebo group will take an equivalent number of identically matched placebo tablets (one per day) by oral administration once daily at bedtime for 6 weeks.
Duration of Study: Each subject will participate in the study for up to 11 weeks, including up to 2 weeks of screening, 6 weeks of treatment, one end-of-study visit during the week following the last treatment dose, and a final telephone contact ~2 weeks after completing treatment for a safety follow-up.

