study subject. If the same AE occurred on multiple occasions, the highest severity and relationship to investigational product will be assumed. Thus, study participants are not counted multiple times in a given numerator in the calculation of frequencies for a specific AE. Laboratory data, vital signs, ECG results, alcohol breathalyzer results, urine drug test results, and CIWA scores will be reported as summary statistics. The numbers and proportion of subjects who reported CIWA scores ≥ 10 at any time after the start of dosing will be presented. Changes in clinical laboratory tests and vital signs will also be presented as summary statistics of change from baseline. The number and percentage of subjects with a higher ACQ-SF-R score post cue session will be provided by treatment group.

Compliance and Participation Outcomes: Medication compliance is defined as the amount of investigational products taken as a proportion of the total amount prescribed. Compliance will also be evaluated by determining the proportion of subjects who were prescribed ASP8062, reported taking ASP8062 (by AiCure assessment), and had a plasma sample with detectable ASP8062. The participation rate is the percentage of subjects with complete drinking data. Compliance and participation rates will be reported on a weekly basis and across the entire trial duration. Compliance by ASP8062 plasma levels will be reported as number and percentage of subjects with a level above the limit of detection at each time point among subjects who were prescribed ASP8062. Compliance with tablet ingestion will be confirmed by AiCure assessment or subject's self-report, if AiCure data is not available. Descriptive statistics will also be provided.

Baseline Descriptive Statistics: Summaries of the characteristics of the subjects in each of the study groups at baseline will be prepared for the mITT, evaluable, and safety analysis sets. Baseline characteristics will be compared between the ASP8062 group and placebo group using appropriate statistical methods.

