**Table 1: Schedule of Assessments**

Study Phase	Screening	Treatment					End of Study a	Follow-up Call
Clinic Visit #	1	2	3	4	5	6	7	
Study Week (Days) b	-2 to -1 (-14 to -1)	1 (1 to 7)	2 (8 to 14)	3 (15 to 21)	4 (22 to 28)	5 (29 to 35)	7 (43 to 49)	9 (57 to 63)
Informed Consent	X							
Alcohol Breathalyzer	X	X	X	X	X	X	X	
Urine Drug Test c	X	X	X	X	X	X	X	
Locator Form	X	Update	Update	Update	Update	Update	Update	
Demographics	X							
Medical History	X	Update						
Physical Exam	X	Update						
Body Weight	X				X		X	
MINI	X							
C-SSRS		X	X	X	X	X	X	
Clinical Chemistry d	X				X		X	
Hematology e	X				X		X	
Medical Urinalysis f	X				X		X	
Pregnancy Test	X	X					X	
Birth control methods (all subjects)	X	Update	Update	Update	Update	Update	Update	

Study Phase	Screening	Treatment					End of Study a	Follow-up Call
Clinic Visit #	1	2	3	4	5	6	7	
Study Week (Days) b	-2 to -1 (-14 to -1)	1 (1 to 7)	2 (8 to 14)	3 (15 to 21)	4 (22 to 28)	5 (29 to 35)	7 (43 to 49)	9 (57 to 63)
Vital Signs g	X	X	X	X	X	X	X	
Eligibility Checklist	X	X						
Drinking Goal	X							
ECG	X				X		X	
Prior and Concomitant Meds	X	X	X	X	X	X	X	X
CIWA-AR	X	X	X	X	X	X	X	X
Screening Cue Reactivity Session: VAS Scales	X							
Randomization		X (Day 1)						
Blood for Drug Concentration					X		X	
Drug compliance/ accountability/ Review AiCure		Dispense Day 1	X	X	X	X	X	
AEs (open ended question)		X	X	X	X	X	X	X
Brief Telephone Interview h		once during the week	once during the week	As needed if the subject misses a clinic visit				
Take Control		X	X	X	X i	X	X	
Treatment Cue Reactivity Session: VAS Scales				X				

Study Phase	Screening	Treatment					End of Study a	Follow-up Call
Clinic Visit #	1	2	3	4	5	6	7	
Study Week (Days) b	-2 to -1 (-14 to -1)	1 (1 to 7)	2 (8 to 14)	3 (15 to 21)	4 (22 to 28)	5 (29 to 35)	7 (43 to 49)	9 (57 to 63)
TLFB	X	X	X	X	X	X	X	
Brief Drinking Questionnaire	as needed							
Exit Interview							X	
ACQ-SF-R	2X pre/post cue session			2X pre/post cue session				
PACS		X	X	X	X	X	X	
Cigarette smoking quantity/frequency and nicotine use		X				X	X	
PSQI		X				X	X	
POMS		X				X	X	
PROMIS Alcohol Negative Consequences		X					X	
Hyperkatifeia Scale		X						
Treatment Referral							X	
Follow-Up Telephone Interview								X
Final Subject Disposition								X

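### At Week 7 the day-before AiCure rule in shell Tables 10 and 11 can be met only by a Day 43 visit, so the Week 7 and Overall agreement results reflect visit timing rather than adherence

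*SAP*

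**What the plan says.** - **Dosing.** The protocol synopsis (investigational product entry) gives "25 mg tablet of ASP8062 by oral administration once daily at bedtime for 6 weeks". In the SAP 3.2 Schedule of Assessments the drug row reads "Dispense Day 1". Shell Table 2 notes that the "maximum prescribed is 42 tablets".
- **Sampling.** In the same schedule, the row "Blood for Drug Concentration" is marked at Week 4 (Days 22 to 28) and Week 7 (Days 43 to 49). Footnote a also allows the end-of-study assessments at a final visit after early discontinuation.
- **Comparison.** Shell Table 10 sets plasma Yes/No against AiCure Yes/No for Week 4, Week 7 and Overall, with chi-square and kappa. The AiCure condition is "pill count must = 1, on the day before the blood sample was drawn". Table 11 repeats it for evaluable subjects.
- **Plasma summaries.** SAP 9.7 reports the number and "percentage of subjects with a level above the limit of detection at each time point". For the descriptive statistics it leaves out samples below quantitation and says "the N will reflect the number with a detectable level at each timepoint". The protocol (Compliance and Participation Outcomes) bases the detection percentage on subjects prescribed ASP8062.

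**The concern.** The condition suits a sample drawn during treatment, when the day before is always a dosing day. The Week 7 sample is drawn after treatment ends. For most permitted visit days no tablet was scheduled on the day before, so AiCure cannot show one, however well the subject adhered. The same rule feeds the Overall row, so the Week 7 error is carried into the pooled result.

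This table is where the plan tests whether AiCure records and drug levels agree. Near-zero agreement at Week 7 would cast doubt on the AiCure data, or on adherence, for a reason that has nothing to do with either.

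**Working it through.** **1. Last dosing day.** 6 weeks × 7 days × 1 tablet = 42, which reproduces the figure in shell Table 2. With the first tablet on Day 1 (assumed from Day 1 dispensing), the last is on Day 42.

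**2. Visit days that can meet the rule.** A draw on day d qualifies only if d − 1 lies within Days 1 to 42.

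| Visit | Draw days d | d − 1 | Days that qualify |
|---|---|---|---|
| Week 4 | 22–28 | 21–27 | 7 of 7 |
| Week 7 | 43–49 | 42–48 | 1 of 7 (Day 43) |

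The Week 7 draw is 1 to 7 days after the date of the last scheduled tablet. With the planned 30 subjects in the arm, all fully adherent and visits spread evenly (assumed), AiCure would be Yes for 30 × 1/7 = 4.3 and No for 30 × 6/7 = 25.7.

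**3. Effect on Week 7 kappa.** Let a be the adherent share and s the share of adherent subjects seen on Day 43. Assume that plasma classifies everyone correctly and that non-adherent subjects are No on both measures.

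- Observed agreement: po = a·s + (1 − a)
- Chance agreement: pe = a·(a·s) + (1 − a)·(1 − a·s)
- Kappa = (po − pe)/(1 − pe)

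With a = 0.90 and s = 1/7, a·s = 0.129, po = 0.229 and pe = 0.116 + 0.087 = 0.203. Kappa = 0.026/0.797 = 0.03. If the AiCure condition is anchored to Day 42, s = 1 and kappa = 1.00.

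| Share of adherent subjects seen on Day 43 (a = 0.90) | Week 7 kappa |
|---|---|
| 0 | 0.00 |
| 1/7 | 0.03 |
| 1/2 | 0.17 |
| 1 | 1.00 |

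At s = 1/7, kappa is 0.06 for a = 0.80 and 0.02 for a = 0.95.

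**4. Overall row.** Assume equal numbers of Week 4 and Week 7 samples and the a = 0.90, s = 1/7 case, with perfect agreement at Week 4. Observed agreement is (1 + 0.229)/2 = 0.614. The AiCure Yes share is (0.900 + 0.129)/2 = 0.514. Chance agreement is 0.9 × 0.514 + 0.1 × 0.486 = 0.511. Kappa = (0.614 − 0.511)/(1 − 0.511) = 0.21, where the correct value is again 1.00.

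**5. Table 8 denominator, a separate matter.** The shell has one N column beside both % > LLD and the mean. If 20 of 30 samples were detectable (illustrative), the percentage is 20/30 = 66.7%. Using the detectable-only N from SAP 9.7 as the base would give 20/20 = 100%.

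**The case against.** The strongest reply is that this is a faulty condition in one shell and its repeat. No efficacy analysis uses it. Table 4 compliance is tablets taken over tablets prescribed, the mITT and evaluable definitions use neither plasma nor the day-before rule, and the Week 4 sample, the one closer to the Week 3 primary endpoint, is unaffected. The rule does not fail completely either: a Day 43 visit after a bedtime tablet on Day 42 meets it. All of this stands and limits the weight of the point. It does not rescue the Week 7 and Overall rows.

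A reader might go further in four ways that the documents do not support.

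- *That the detectable-only N causes adherent subjects to be scored non-compliant.* The effect runs the other way: dropping undetectable samples can only hide non-compliance. That N is also in SAP 9.7, not in Table 10.
- *That % > LLD will be 100% whatever the truth.* This requires a programmer to apply the summary-statistics N to the percentage, against the denominator in the protocol. What remains is that Table 8 should say which base it uses.
- *That Week 7 will show low detection in a fully adherent arm.* The documents give no half-life, and the Table 10 plasma cut-off is still a placeholder. Washout is possible, but its size cannot be stated.
- *That an AiCure failure is counted as missed tablets, or alters the evaluable set.* No text says so. The protocol falls back on self-report "if AiCure data is not available", and although SAP 9.7 does not repeat this, the evaluable definition does not name AiCure at all.

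**Conclusion.** The point holds for the Week 7 and Overall rows of shell Tables 10 and 11. From the plan's own day count, the AiCure condition can be met on 1 of 7 permitted Week 7 visit days. Adherent subjects seen on the other six fall in AiCure No by construction, and the cell counts, chi-square and kappa follow. The misclassification is on the AiCure side.

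The day count rests on a Day 1 start. A later start with all 42 tablets still taken would make a few later visit days valid. The kappa of about 0.03 rests on the assumed adherence, plasma accuracy and even spread of visits. The proportion of adherent subjects affected is 0 if all are seen on Day 43 and 100% if none are. The consequence is a misleading agreement table; the efficacy results and the main compliance ratio are untouched.

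**What to change.** - **Tables 10 and 11, end-of-study sample.** Compare plasma with AiCure on the subject's last scheduled dosing day before the draw: Day 42 for completers, and the subject's own last scheduled dosing day for those who discontinue early and are sampled under footnote a. A fixed Day 42 anchor would misclassify the latter.
- **Same tables.** Show days from last dose to draw. Keep kappa by visit, since the Week 4 value is valid, and present Overall only after re-anchoring.
- **SAP 9.7 and Table 8, Week 7.** Present % > LLD by days since last dose, with a note that it may also reflect washout.
- **Table 8 footnote.** State that the denominator of % > LLD is ASP8062 subjects, as in the protocol, or those with an assayed sample. Give a separate n for means among quantifiable samples.

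The cost is SAP wording and shell edits, with no extra samples or visits. Listing 22 already holds daily AiCure records and Listing 39 the date and time of each draw.
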